## **12 HUMAN SUBJECTS**

Each study participant or a LAR must sign and date an informed consent form. Approval for this feasibility trial will be obtained from the University of Pittsburgh Human Research Protection Office (HRPO), which will serve as the single IRB, before any subject is entered into the study.

### **12.1 SELECTION OF SUBJECTS**

Federal regulations at 45 CFR 46(a)(3) require the equitable selection of subjects. The ICUs at the UPMC and Mayo Clinic will be screened daily to determine if any patient meets inclusion and exclusion criteria. Data that have been collected as part of the routine management of the subject will be reviewed to determine eligibility. No protocol-specific tests or procedures will be performed as part of the screening process. If any subject meet criteria for study enrollment, then the attending physician will be asked for permission to approach the patient or his/her LAR for informed consent. Study exclusion criteria neither unjustly exclude classes of individuals from participation in the research nor unjustly include classes of individuals from participation in the research. Hence, the recruitment of subjects conforms to the principle of distributive justice.

### **12.2 JUSTIFICATION OF INCLUDING VULNERABLE SUBJECTS**

The present research aims to investigate the feasibility of alternative UFNET strategies for critically ill patients. Since the subjects enrolled in this clinical trial will have fluid overload and one or more organ system failure (e.g., respiratory and renal failure) it is anticipated that most of these patients will have impaired decision-making capability. This study cannot be conducted if limited to enrolling only those subjects with retained decision-making capacity. Hence, subjects recruited for this trial are not being unfairly burdened with involvement in this research simply because they are easily available.

### **12.3 INFORMED CONSENT**

Federal regulations 45 CFR 46.111 (a) (5) require that informed consent be sought from each prospective subject or the subject's LAR. We anticipate almost all consents will be from the subject's LAR, and thus the remainder of this section will focus on LARs. The one obtaining consent is responsible for ensuring that the LAR understands the risks and benefits of participating in the study and answering any questions the LAR may have throughout the study and sharing any new information in a timely manner that may be

relevant to the LAR's willingness to permit the subject's continued participation in the trial. The consenter will make every effort to minimize coercion.

All study participants or their LARs will be informed of the objectives of the study and the potential risks. Prior to obtaining informed consent the patient and/or LAR will also be provided a study brochure. The informed consent document will be used to explain the risks and benefits of study participation to the LAR in simple terms before the patient is entered into the study, and to document that the LAR is satisfied with his or her understanding of the risks and benefits of participating in the study and desires to participate in the study. The investigator is responsible for ensuring that informed consent is given by each LAR. The process of informed consent between a study attending physician investigator or study resident/fellow physician and the patient or LAR may occur face-to-face either in-person or virtually via a remote electronic communications platform (e.g., via ZOOM/Teams) due to restrictions because of hospital COVID-19 protocols. This includes obtaining the appropriate signatures and dates on the informed consent document prior to the performance of any protocol procedures. In case of virtual consent with LAR, appropriate electronic signatures from LAR, witness, and/or attending physician investigator or study resident/fellow physician will be obtained via an approved electronic consent platform.

To obtain informed consent, the following information shall be provided to each patient or patient's LAR:

- a. The name of the study.
- b. The name of the Principal Investigator.
- c. An explanation that the study involves research.
- d. An explanation that the purpose of the study is to determine feasibility of maintaining slow or fast fluid removal, and whether a particular strategy of fluid removal is associated with less fluid overload and complications.
- e. An explanation that the active treatment portion of the study will last up to 28 days from study enrollment.
- f. A description of the restrictive and liberal UFNET rate strategies
- g. A description of benefits and risks associated with restrictive and liberal UFNET strategies
- h. A description of randomization at the ICU level.
- i. A description that participation in the study may require longer or shorter times on dialysis treatment with fluid removal.
- j. A description that the patient's medical record number will be used to identify records and to track the patient during hospital stay.
- k. A description that the alternative to participation in this study will be to receive fluid removal during kidney replacement therapy (dialysis) as per clinician discretion and not as part of the study.
- l. A description that all records will be kept confidential.
- m. An explanation of whom to contact for answers to questions about the research and about research subject's rights.
- n. An explanation of whom to contact in the event of research-related injury.

- o. A statement that participation in the study is voluntary and that a decision not to participate or to withdraw from the study after initially agreeing to participate will involve no penalty, loss of benefits or reduction in access to medical care.
- p. A statement that there will be no cost for the treatments provided as part of this study.
- q. A statement that there will be no payment for participation in this study.

## 12.4 CONTINUING CONSENT

Subjects for whom consent was initially obtained from a LAR, but who subsequently regain decision-making capacity while still in hospital within the 28d post intervention period, will be approached for consent for continuing participation, including continuance of data acquisition. The consent form signed by the LAR will reflect that such consent will be obtained.

## 12.5 WITHDRAWAL OF CONSENT

Patients may withdraw or be withdrawn (by the LAR) from the trial at any time without prejudice. Data recorded up to the point of withdrawal will be included in the trial analyses unless consent to use their data has also been withdrawn. If a patient or LAR requests termination of the trial intervention during the treatment period, the intervention will be stopped but the patient will continue to be followed up as part of the trial. If a patient or LAR withdraws consent during the trial treatment, the trial intervention will be stopped but permission will be sought to access medical records for data related to the trial. If a patient or LAR wishes to withdraw from the trial after completion of trial treatment, permission to access medical records for trial data will be sought.

## 12.6 IDENTIFICATION OF LEGALLY AUTHORIZED REPRESENTATIVES

Many of the patients approached for participation in this research protocol will invariably have limitations of decision-making abilities due to their critical illness. Hence, most patients will not be able to provide informed consent. Accordingly, informed consent will be sought from the potential subject's LAR.

Regarding proxy consent, the existing federal research regulations ("the Common Rule") states at 45 CFR 46.116 that "no investigator may involve a human being as a subject in research..... unless the investigator has obtained the legally effective informed consent of the subject or the subject's legally authorized representative"; and defines at 45 CFR 46.102 (2) a legally authorized representative as "an individual or judicial or other body authorized under applicable law to consent on behalf of a prospective subject to the subject's participation in the procedures(s) involved in the research." The Office of Human Research Protections (OHRP) defined examples of "applicable law" as being state statutes, regulations, case law, or formal opinion of a State Attorney General that addresses the issue of surrogate consent to medical procedures. Such "applicable law" could then be considered as empowering the LAR to provide consent for subject participation in the research.

According to a previous President's Bioethics Committee (National Bioethics Advisory Committee [NBAC]), an investigator should accept a relative or friend of the potential subject who is recognized as an LAR for purposes of clinical decision making under the law of the state where the research takes place. Finally, OHRP has stated in their determination letters that a surrogate could serve as a LAR for research decision making if such an individual is authorized under applicable state law to provide consent for the "procedures" involved in the research study.

In the state of Pennsylvania, the following individuals may be considered LARs of a potential research subject and capable of providing surrogate consent:

- A court-appointed guardian authorized in a current court order to consent to the subject's participation in the research.
- A health care agent appointed by the subject in a power of attorney.
- A "health care representative" when the individual cannot speak for his/herself and where there has been no guardian appointed by the court and no health care power of attorney designated (PA Act 169).
- Any of the following relatives, in descending order of priority, who is reasonably available, may also act as the subject's health care representative:
  - a. The spouse (unless an action for divorce is pending).
  - b. Adult children (18 years of age or older).
  - c. A parent.
  - d. An adult sibling.
  - e. An adult grandchild.
  - f. An adult who has knowledge of the potential research subject's preferences and values, including but not limited to religious and moral beliefs, who is able to assess how the patient would make decisions.

## 12.7 JUSTIFICATION OF SURROGATE CONSENT

According to the Belmont Report, respect for persons incorporates at least two ethical convictions; first, that individuals should be treated as autonomous agents, and second, that persons with diminished autonomy are entitled to protection. One method that serves to protect subjects is restrictions on the participation of subjects in research that presents greater than minimal risks. Commentators and research ethics commissions have held the view that it is permissible to include incapable subjects in greater than minimal risk research as long as there is the potential for beneficial effects and that the research presents a balance of risks and expected direct benefits similar to that available in the clinical setting. Commentators and research ethics commissions have held the view that it is permissible to include incapable subjects in greater than minimal risk research as long as there is the potential for beneficial effects and that the research presents a balance of risks and expected direct benefits similar to that available in the clinical setting.

Several U.S. tasks forces have deemed it is permissible to include incapable subjects in research. For example, the American College of Physicians document allows surrogates to consent to research involving incapable subjects only "if the net additional risks of

participation are not substantially greater than the risks of standard treatment". Finally, NBAC stated than an IRB may approve a protocol that presents greater than minimal risk but offers the prospect of direct medical benefits to the subject, provided that "the potential subject's LAR gives permission.....". Several U.S. tasks forces have deemed it is permissible to include incapable subjects in research. For example, the American College of Physicians document allows surrogates to consent to research involving incapable subjects only "if the net additional risks of participation are not substantially greater than the risks of standard treatment". Finally, NBAC stated than an IRB may approve a protocol that presents greater than minimal risk but offers the prospect of direct medical benefits to the subject, provided that "the potential subject's LAR gives permission.....". Consistent with the above ethical sensibilities regarding the participation of decisional incapable subjects in research and the previous assessment of risks and benefits in the previous section, the present trial presents a balance of risks and potential direct benefits that is similar to that available in the clinical setting.

## 12.8 ADDITIONAL SAFEGUARDS FOR VULNERABLE SUBJECTS

The present research will involve subjects who might be vulnerable to coercion or undue influence. As required in 45 CFR 46.111 (b), we will use additional safeguards to protect the rights and welfare of these subjects. Such safeguards might include but are not limited to: i.) assessment of the potential subject's capacity to provide informed consent; ii.) the availability of the LAR to monitor the subject's subsequent participation and withdrawal from the study; and iii.) augmented consent processes. The specific nature of the additional safeguards will be left to the discretion of the Human Research Protection Office.

## 12.9 CONFIDENTIALITY

Federal regulations at 45 CFR 46 111 (a) (7) requires that when appropriate, there are adequate provisions to protect the privacy of subjects and to maintain the confidentiality of data. To maintain confidentiality, all evaluation forms, and reports will be identified only by a coded number. The coded number will be generated by a computer, and only the study team will have access to the codes. All records will be kept in a locked, password protected computer. All computer entry and networking programs will be done with coded numbers only. All paper case report forms will be maintained inside a locked office. Study information will not be released without the written permission of the patient, except as necessary for monitoring by the institutional Data and Safety Monitoring Board.

## 13 SAFETY MONITORING

### 13.1 ADVERSE EVENTS

A clinical trial adverse event (AE) is defined as any untoward medical event temporally associated with the use of drug or study procedure in humans, whether or not it is considered related to a study intervention or study procedure. Assuring patient safety is an essential component of this protocol and the Principal Investigators have the primary responsibility for the safety of the individual participants. Thus, the Principal Investigators

will monitor for all AEs from study enrollment until ICU discharge or day 28, whichever occurs first.

Following study enrollment, AEs occurring after the patient received the study interventions will be evaluated at the two clinical sites by the Principal Investigators. Investigators will assess if there is a reasonable possibility that the study procedure caused the event, based on the criteria outlined in [Appendix G1](#).

If a patient's study treatment is discontinued because of an AE, the study investigator must report the circumstances and data leading to discontinuation of treatment in the AE case report forms. AEs will be considered related or possibly related to study treatment only up to 24 hours following discontinuation of CKRT. AEs occurring after discontinuation of CKRT and after transition to IHD will not be considered related to study interventions.

Investigators will also consider if the event is unanticipated or unexplained given the patient's clinical course, previous medical conditions, and concomitant medications as outlined in [Appendix G2](#). An adverse event is considered "unanticipated" if it is not listed in the study protocol (21 CFR 312.32(a)).

The following adverse events will be collected in the case report forms:

- Serious adverse events
- Non-serious adverse events that are considered by the investigator to be related to study intervention or study procedures or of uncertain relationship ([Appendix G](#))
- New onset hypotensive and hypertensive episodes, cardiac arrhythmias, considered by the investigator to be related to rate of fluid removal during CKRT, or of uncertain relationship
- Emergent use of rescue UFNET rates with rates higher than the assigned treatment arm
- Severe hypophosphatemia, hypokalemia, hypocalcemia
- CKRT system clotting, clogging, downtime, and discontinuation of fluid removal due to patient instability.
- Inability to close surgical wounds due to edema
- New organ dysfunction such as diastolic and systolic dysfunction on echocardiogram; pulmonary edema on chest X ray; ileus, bowel ischemia, anastomotic break down; wound infection, and pressure ulceration; arterial and venous thrombosis; severe anemia requiring red cell transfusions, and severe thrombocytopenia requiring platelet transfusions.
- New secondary infections

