## 7 STUDY PROCEDURES

Clinical trials should be conducted in a setting reflective of best practice that can be clearly described and reproduced in a clinical non-trial setting. Thus, we will ensure that there are no imminent indications for emergent and rapid UFNET rates after discussing with the attending physician. Blinding is not feasible due to the nature of the intervention. To calculate the UFNET rate, we will use patient predicted body weight (PBW) determined from patient height and has been used in several NIH sponsored ICU trials ([Appendix A](#)).

Close oversight will be provided by ICU attending and/or designee. Before initiation of UFNET, we will ensure i.) the CKRT is operational; ii.) a study investigator or designee will assess the hemodynamic appropriateness for initiation of UFNET using the following as guidelines: MAP  $\geq$ 65 mm Hg and no fluid bolus has been administered or new vasopressor started or vasopressor dose increased in the last hour; iii.) study investigator or designee will discuss with the attending physician to ensure there are no emergency indications for fluid removal; and iv.) UFNET according to protocol will be initiated within 24 hours of enrollment in both groups.

To calculate the correct and dynamic UFNET rate for the two intervention groups, we will use a web-based UFNET rate calculator located on a password protected secure database accessed via a tablet computer, desktop computer, or computer on wheels. This UFNET rate calculator will be programmed to automatically calculate the net fluid removal rate based on the allocation to the intervention group, predicted body weight, and rate of fluids infused into the patient. At all times, we will emphasize that the clinicians retain complete decision-making authority with respect to selecting and titrating the UFNET rate, if the protocol cannot be followed for patient related reasons. **Thus, the final decision to set a UFNET rate will be at the discretion of the treating clinician.**

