#### 13.3.1 IRB REPORTING

An AE or SAE is judged to be reportable to University of Pittsburgh HRPO, if it meets ALL of the following: i.) unanticipated in terms of nature, severity, or frequency; ii.) related or possibly related to study intervention; iii.) places subjects or others at a greater risk of physical, psychological, economic or social harm than was previously known or recognized. If the AE is judged to be reportable to the IRB based on above criteria, then the study team at the University of Pittsburgh will report to the HRPO within 10 working days. If it is an SAE and meets the above criteria, the study team will report to the HRPO within 24 hours.

All SAEs that meet above criteria and occurring at Mayo Clinic must be reported to the study team at University of Pittsburgh within 24 hours. All AEs that meet above criteria and occurring at Mayo Clinic must be reported within 5 working days to the team at University of Pittsburgh. The study team at University of Pittsburgh will then report all AE and SAE to the University of Pittsburgh HRPO within timelines shown in Table 7. The AEs that comprise the safety outcomes will be included in outcome reporting and will not be reported a second time as AEs or SAE.

At both clinical sites the study personnel must alert the Principal Investigator of any serious and study procedure-related adverse event within 24 hours of investigator/coordinator awareness of the event. Please note that most AEs will not meet the definition of an Unanticipated Problem Involving Risk to Subjects or Others and need not be reported to the HRPO. Expected AEs or AEs which are determined by the investigator to be unrelated to the research intervention need not be reported to the IRB. The flow chart below provides an algorithm for determining whether an AE meets the definition of an unanticipated problem involving risk to subjects or others and whether it needs to be reported to HRPO.

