## G. ADVERSE EVENT REPORTING AND UNANTICIPATED PROBLEMS

### G1. DETERMINING RELATIONSHIP OF ADVERSE EVENTS TO STUDY PROCEDURES

Investigators will be asked to grade the strength of the relationship of an adverse event to study procedures as follows:

- Definitely Related: The event follows: a) A reasonable, temporal sequence from a study procedure; and b) cannot be explained by the known characteristics of the patient's clinical state or other therapies; and c) evaluation of the patient's clinical state indicates to the investigator that the experience is definitely related to study procedures.
- Probably or Possibly Related: The event should be assessed following the same criteria for "Definitely Associated". If in the investigator's opinion at least one or more of the criteria are not present, then "probably" or "possibly" associated should be selected.
- Probably Not Related: The event occurred while the patient was on the study but can reasonably be explained by the known characteristics of the patient's clinical state or other therapies.
- Definitely Not Related: The event is definitely produced by the patient's clinical state or by other modes of therapy administered to the patient.
- Uncertain Relationship: The event does not meet any of the criteria previously outlined.

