#### 3.5.3 SAFETY OUTCOMES

1. No. of intradialytic hypotensive episodes
2. No. of intradialytic hypertensive episodes
3. No. of intradialytic new onset cardiac arrhythmias including supraventricular tachycardia, bradycardia, atrial fibrillation, ventricular tachycardia, ventricular fibrillation, and cardiac arrest
4. No. of participants with emergent use of rescue  $UF_{NET}$  with rates higher than the assigned treatment arm
5. No. of participants with severe hypophosphatemia ( $<0.5$  mg/dL)
6. No. of participants with severe hypokalemia ( $<3.0$  mg/dL)
7. No. of participants with severe hypocalcemia ( $<1.90$  mg/dL or ionized calcium  $<0.90$  mmol/L)
8. No. of episodes of stopping CKRT due to filter clotting or clogging
9. No. of participants with discontinuation of  $UF_{NET}$  due to hemodynamic instability
10. No. of participants in whom surgical wounds are left open due to edema
11. No. of participants with new organ dysfunction
12. No. of participants with worsening of systolic or diastolic cardiac function on echocardiogram
13. No. of participants with worsening of pulmonary edema on chest X Ray and/or CT scan
14. No. of participants with worsening of ileus on abdominal X Ray and/or CT scan
15. No. of participants with bowel ischemia or anastomotic breakdown based on intraoperative findings
16. No. of participants with pressure ulcerations
17. No. of participants with new wound infections
18. No. of participants with new arterial or venous thrombosis
19. No. of participants with severe anemia requiring red cell transfusions

20. No. of participants with severe thrombocytopenia requiring platelet transfusions
21. No. of participants with new secondary infections

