#### 5.2.2.1 *Intradialytic hypotension*

Intradialytic hypotension will be defined as a new MAP  $<65$  mmHg, SBP  $<90$  mmHg or a decline in SBP  $>40$  mmHg, and/or a  $>30\%$  increase in dose of existing vasopressors, initiating a new vasopressor, administration of fluid bolus, or discontinuation of fluid removal with a goal to maintain (MAP)  $\geq 65$  mmHg, systolic blood pressure (SBP)  $\geq 90$  mmHg.

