#### *5.2.2.7 New organ dysfunction due to fluid overload*

New and worsening organ dysfunction will be assessed based on SOFA scoring. For instance, a patient with CV SOFA score of 3 at study initiation and now has score of 4 will be counted as worsening CV dysfunction. We will also capture new diastolic/systolic dysfunction on echocardiogram, pulmonary edema on chest X ray/CT scan, ileus on abdominal X ray/CT scan, bowel ischemia and anastomotic breakdown on CT scan/OR, transaminitis or hyperbilirubinemia; delirium using delirium scores on medical records, poor wound healing, wound infection, and pressure ulceration per nursing records, new onset arterial and venous thrombosis as documented by imaging and clinical examination, and anemia, hemolysis and thrombocytopenia as documented in the laboratory studies.

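### Protocol 13.1 lets an unblinded relatedness judgement decide which non-serious hypotensive, hypertensive and arrhythmic episodes reach the case report form; Appendix F1 and the SAP have no such condition, and neither document says which record is analysed

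*Protocol*

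**What the plan says.** **The collection rule.** Protocol 13.1 lists the adverse events to be entered in the case report forms. One bullet covers "New onset hypotensive and hypertensive episodes, cardiac arrhythmias, considered by the investigator to be related to rate of fluid removal during CKRT". The full condition is "considered by the investigator to be related to rate of fluid removal during CKRT, or of uncertain relationship". The bullets on rescue ultrafiltration, electrolytes, circuit problems, open wounds, organ dysfunction and secondary infection carry no such condition.

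**The grades.** Protocol Appendix G1 has five: definitely related, probably or possibly related, probably not related, definitely not related, and a residual one: "Uncertain Relationship: The event does not meet any of the criteria previously outlined".

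**Blinding.** Protocol section 7: "Blinding is not feasible due to the nature of the intervention".

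**The schedule.** Protocol Appendix F1 marks hypotensive and hypertensive episodes, and cardiac arrhythmias, as required from day 0 to day 28. The footnotes on those rows restrict collection by dialysis modality and time, not by cause.

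**The analysis.** SAP 3.5.3 lists "No. of intradialytic hypotensive episodes" and the matching counts for hypertension and arrhythmia. The definitions are clinical. For example, "Intradialytic hypotension will be defined as a new MAP" opens a list of blood-pressure thresholds and interventions (SAP 5.2.2.1). Nothing in 5.2.2.1 to 5.2.2.3 asks whether the fluid-removal rate caused the event.

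**Reporting.** Protocol 13.3.1 describes the safety outcomes as adverse events that go through outcome reporting and "will not be reported a second time as AEs or SAE".

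**The concern.** The three outcomes are defined one way for analysis and can be collected another way at the bedside. A coordinator working from 13.1 and one working from Appendix F1 would record different sets of episodes.

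The difference need not be neutral between arms. The person grading relatedness knows the ICU's current strategy and the protocol's central hypothesis, which is that the restrictive strategy brings fewer complications, hypotension and arrhythmias among them. The same septic, vasopressor-dependent patient who becomes hypotensive may be graded possibly related in a liberal period and probably not related in a restrictive one.

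Three uses of the data depend on the answer: the between-arm comparison in SAP Table 3; the hypotension frequency that the DSMB reviews under protocol 13.3.2; and the provision there that the ethics office be notified if the DSMB finds a higher overall adverse-event rate in one group.

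**Working it through.** The plan gives no figure to reproduce here. The check is a reconciliation of the text, followed by an illustration of scale.

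**Step 1. What the 13.1 bullet leaves out.**

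| Grade (Appendix G1) | Non-serious episode, 13.1 bullet | Appendix F1 | SAP 5.2.2.1 to 5.2.2.3 |
|---|---|---|---|
| Definitely related | collected | collected | counted |
| Probably or possibly related | collected | collected | counted |
| Uncertain | collected | collected | counted |
| Probably not related | left out | collected | counted |
| Definitely not related | left out | collected | counted |

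Serious episodes are outside this table, because protocol 13.2 collects them whatever the investigator thinks of causation. The probably-not grade applies when the patient's condition or other treatment can reasonably explain the event. In this population that could fit many hypotensive episodes and arrhythmias, so the excluded rows need not be small.

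**Step 2. Which record feeds the SAP counts.**

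- Pointing to the 13.1 record: its bullets follow the safety-outcome list in 5.8.3 closely, and 13.3.1 calls the safety outcomes adverse events.
- Pointing to unfiltered data: Appendix F1 requires the episodes. Section 8.3.2 says the data recorded on the Appendix F schedule are the basis for assessing safety and between-group differences.
- Not decisive: the any-episode rule in 8.3.1 covers study start-up only. The measurements itemised in 8.3.2 include no count of hypotensive, hypertensive or arrhythmic episodes. Appendix F1 does not say what qualifies as an episode.

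No sentence in either document settles it.

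**Step 3. Scale, if the 13.1 record were used.** The capture fractions below are assumptions; the documents give none. Let c_R and c_L be the fractions of episodes recorded in the restrictive and liberal arms, with equal true rates.

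- *Episode counts* (SAP 3.5.3). Recorded ratio = c_R / c_L, whatever the background rate. With c_R = 0.8 and c_L = 1.0 the ratio is 0.80; with 0.9 and 1.0 it is 0.90; with equal capture it is 1.
- *Patients with at least one episode* (the comparison behind the P values in SAP Table 3). If a fraction p of patients have episodes, k each, recorded independently, the recorded fraction is p × [1 − (1 − c)^k]. For p, protocol 5.2.5 gives 43% (hypotension in the first hour) and 64.6% (early hypotension). For k = 1, c_R = 0.8 and c_L = 1.0:
  - p = 0.43: 0.43 × 0.8 = 0.344 against 0.430, a gap of 8.6 points
  - p = 0.646: 0.646 × 0.8 = 0.517 against 0.646, a gap of 12.9 points
- For k = 3 and the same captures, 1 − 0.2³ = 0.992:
  - p = 0.43: 0.427 against 0.430, a gap of 0.3 points
  - p = 0.646: 0.641 against 0.646, a gap of 0.5 points

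The distortion on the patient scale therefore runs from negligible to more than ten points, depending on how often episodes recur. On the episode scale it does not shrink with recurrence.

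**The case against.** The strongest reply is that this is a wording mismatch and not a demonstrated bias. Much of it stands.

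- A reader who stops at the word related might infer that only episodes judged related are recorded. The clause also admits uncertain ones, and serious episodes come in regardless.
- A reader might infer that the safety comparison is in fact filtered by investigator opinion. The documents do not establish that. Appendix F1 requires the episodes unfiltered, 8.3.2 ties between-group safety assessment to the schedule data, and the SAP adjudicates by criteria. Nor does either document designate a key safety outcome.
- The background rates are for early hypotension in other cohorts. The 64.6% figure uses a definition that differs from SAP 5.2.2.1, for instance a MAP cut-off of 60 mmHg where the SAP uses 65. Multiplying a patient-level incidence by an episode-level capture fraction overstates the effect when episodes recur, as step 3 shows.
- Protocol 11.3 says the trial is not powered for differences in adverse events, and the SAP leaves the safety P values unadjusted for multiplicity.
- It is tempting to see a second causal filter in the SAP heading "New organ dysfunction due to fluid overload" (5.2.2.7). The text under that heading scores SOFA worsening with no test of cause, and it also captures bowel ischemia and thrombosis. At most the heading needs tidying; it is not part of this point.

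Two things survive. Low power does not excuse a collection rule that depends on the arm, since the descriptive counts are what a feasibility trial passes on to the next trial. And the documents never name the unfiltered record as the source.

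**Conclusion.** The inconsistency is real and should be fixed. For non-serious episodes, protocol 13.1 makes collection depend on an unblinded judgement of relatedness, which neither Appendix F1 nor the SAP applies. Whether this reaches the analysis depends on an unstated choice of source record, so bias is a risk left open and not an established fault. Neither its direction nor its size can be derived from the documents. The figures in step 3 rest on assumed capture fractions, equal true rates and independent recording, and they ignore clustering. They show only that the effect could range from nil to material. If capture were equal in both arms the comparison would not be distorted in ratio, but the recorded counts would still fall short of the outcome the SAP defines.

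**What to change.** 1. In protocol 13.1, delete the relatedness condition from the bullet on hypotension, hypertension and arrhythmia.
2. Record relatedness for each episode in a separate field that does not decide whether the episode is collected.
3. State in both documents that safety outcomes 1 to 3 are derived, in both arms, from all episodes meeting SAP 5.2.2.1 to 5.2.2.3, and name the record used, including for DSMB reports.
4. Reconcile the time window in the same edit. SAP 5.2.2 adjudicates to 12 hours after CKRT stops, while protocol 13.1 and Appendix F1 use 24 hours.

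The cost is one bullet in the protocol, a source statement in each document and a form instruction, with slightly more events recorded. Appendix F1 already schedules blood pressure, vital signs and medications. It is best done before data accrue, because episodes left off the form might later be recoverable only by going back to the charts.
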